9.7. Treatment Characteristics

Renal denervation treatment measures such as number of ablation attempts and number of generator codes will be summarized separately for each kidney, and for combined kidneys. Anti-hypertensive medication use will also be summarized at baseline and at each follow-up.

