9.9.8. Additional Objectives

- Quality of Life (QOL) EQ-5D measures.
- Antihypertensive medication usage throughout the study, including escape patients and subjects with medication changes within 6-month follow-up.
- Additional procedural characteristics e.g. treatment duration, frequency of distal renal artery treatment, ablations per vessel, location of ablations, number of ablations per patient and other characteristics will be analyzed to assess their impact on blood pressure.
- Medication adherence will be assessed using results from drug testing, witnessed pill intake and BP protocol deviations. In addition, we will perform analyses to evaluate the effect of medication adherence on blood pressure change.
- Analyses looking at long term imaging will be performed.

RDN vs. control groups will be compared out to 6-months post randomization, prior to the crossover procedure. Statistical comparisons will be performed using the independent samples t-test for continuous endpoints and Fisher's exact test for categorical endpoints. In addition, two-sided 95% confidence intervals of the difference between RDN and control groups will be presented.

RDN vs. crossover vs. non-crossover groups will be compared out to 36 months post-procedure using chi-square tests for categorical data and ANOVA for continuous data.

Changes in continuous measurements from baseline to follow-up within each group will be assessed using paired t-tests. Two-sided 95% confidence intervals of the mean change from baseline will also be presented for each group.

The additional objectives will be analyzed using the ITT study population defined in section 9.1.3.1.

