9.9.9. Win Ratio Analyses

Win Ratio analyses, which use hierarchical composite outcomes to compare the RDN and Control groups [14], will be used to analyze the blood pressure and AH medication data at follow-up. A prospective

secondary efficacy analysis will be performed at 6-months using the win ratio approach. The following endpoints will be included in the hierarchical comparison:

1. 24Hr SBP change from SV2 to 6M using a threshold of 5 mmHg
2. Medication burden (INDEX2) change from SV2 to 6M using a threshold of zero

The win ratio statistic is a generalisation of the non-parametric Wilcoxon rank-sum test for comparing continuous outcomes between 2 independent groups to multiple prioritized endpoints. Every RDN subject is paired with every control subject and analysed using the endpoints specified above.

- a) For every pair:
 - i. Calculate the change in the first endpoint (24Hr SBP) from SV2 to 6-months for the RDN subject (Δ_{RDN}) and the control subject (Δ_{CON})
 - ii. Calculate the pairwise treatment effect for the pair: $\Delta_{\text{P}} = \Delta_{\text{RDN}} - \Delta_{\text{CON}}$
 - iii. Compare Δ_{P} to the specified threshold (5 mmHg)
 - iv. if the RDN subject has a better outcome compared to control subject using this threshold ($\Delta_{\text{P}} \leq -5$) then this results in a "win" for the RDN subject. We stop analyzing this pair and move on to the next
 - v. if the control subject has a better outcome compared to the RDN subject ($\Delta_{\text{P}} \geq +5$) then this results in a "loss" for the RDN subject. We stop analyzing this pair and move on to the next
 - vi. if the pairwise treatment effect is smaller than the threshold ($-5 < \Delta_{\text{P}} < +5$) or if either subject has missing data then this pair results in a "tie"
- b) Only pairs classified as ties for the first endpoint (24Hr SBP) proceed to the second hierarchical endpoint of medication burden change and we repeat step a) above using their medication burden change data and a threshold of zero.

After every pair has been analyzed, the win ratio statistic is calculated as the total number of wins divided by the total number of losses from both endpoints. The win ratio will be presented with a 95% confidence interval and p-value.

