9.11. Subgroup Analyses

Analysis will be carried out for the following subgroups to assess consistency of results.

- Female vs. male gender
- Age at baseline <65 vs. ≥ 65 years
- BMI by tertiles (kg/m²)
- Type 2 diabetics vs. non-diabetics
- Current smokers vs. former smokers vs non-smokers
- Baseline eGFR <60 vs. ≥60 mL/min/1.73 m²
- Obstructive sleep apnea yes vs. no
- US vs. OUS subjects
- US African American vs. US non-African American subjects
- OUS European vs. Japanese vs. Australian subjects
- Baseline ambulatory SBP by tertiles and medians (mmHg)
- Baseline office SBP by tertiles and medians (mmHg)
- Baseline ambulatory heart rate by tertiles and medians (bpm)
- Baseline office heart rate by tertiles and medians (bpm)
- 24-Hour Pulse Pressure <60 vs. ≥60 mmHg (mmHg)
- Orthostatic hypertension at baseline yes vs. no
- Orthostatic tachycardia at baseline yes vs. no
- Baseline plasma renin activity <0.65 vs. ≥0.65 (ng/mL/h)
- Baseline aldosterone-renin ratio by tertiles
- Baseline aldosterone by tertiles (ng/dL)
- Number of ablations performed by tertiles (RDN arm only)
- Total number of ablations performed in branch vessels by tertiles (RDN arm only)
- Total number of ablations performed in main renal artery vessels by tertiles (RDN arm only)
- Total number of 45 second ablations performed by tertiles (RDN arm only)
- Medication adherent vs. non-adherent subjects at screening visit 2 and 6 months (from urine and serum tests)

- Accessory arteries treated yes vs. no
- 1 vs. 2 vs. 3 prescribed AH medication classes at baseline

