12.1. Appendix I: Imputation of Missing Dates

Imputation of Missing AE Onset Date

Valid Portion	Missing Portion	Imputed Value for Missing Portion
Month, Year	Day	Set Day = first day of that month and year, then set the day = later of (New onset date, informed consent date).
Year	Day, Month	Set date = later of (January 1st of that year, informed consent date).
None	Day, Month, Year	Informed consent date.

Imputation of Missing Medication Start Date

Valid Portion	Missing Portion	Imputed Value for missing Portion
Month, Year	Day	Set Day = first day of that month and year
Year	Day, Month	Set date = January 1st of that year
None	Day, Month, Year	SV2 date

Imputation of Missing Medication Stop Date

Valid Portion	Missing Portion	Imputed Value for missing Portion
Month, Year	Day	Set Day = first day of that month and year, then set the day = later of (New date, SV2 date, start date).
Year	Day, Month	Set date = later of (January 1st of that year, SV2 date, start date).

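### Appendix I rounds incomplete medication stop and start dates down without checking visit records, so some drugs still taken at 6 months can be recorded as stopped and some drugs added in follow-up as baseline drugs

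*SAP*

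**What the plan says.** The rules are in SAP Appendix I (12.1).

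- **Stop date, day missing:** "Set Day = first day of that month and year, then set the day = later of (New date, SV2 date, start date".
- **Stop date, day and month missing:** "Set date = later of (January 1st of that year, SV2 date, start date".
- **Start date, day missing:** "Set Day = first day of that month and year", with no comparison with SV2.
- **Start date, day and month missing:** "Set date = January 1st of that year", again with no comparison.
- **Start date wholly missing:** the SV2 date.

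No row refers to the 6-month visit or to whether the drug was recorded as taken at a visit.

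The analyses that can draw on medication dates are:

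- Section 9.7: "Anti-hypertensive medication use will also be summarized at baseline and at each follow-up".
- Section 9.9.8: "Antihypertensive medication usage throughout the study, including escape patients and subjects with medication changes within 6-month follow-up".
- Section 9.11, subgroup: "1 vs. 2 vs. 3 prescribed AH medication classes at baseline".
- Section 9.9.9, second tier of the win ratio: "Medication burden (INDEX2) change from SV2 to 6M using a threshold of zero". Prescribed data are used there only when drug testing is not available.
- Sections 9.1.3.3 and 9.1.3.4 (Per Protocol, Medication Adherence Population 1): drug tests are compared with the antihypertensives prescribed at SV2.

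**The concern.** Rounding a stop date down gives the shortest exposure that the known month or year allows, subject only to the SV2 and start-date floor. A year-only stop can fall back to SV2 itself although the drug was taken through the 6-month visit. The record then shows a reduction that did not happen. Rounding a start date down without looking at SV2 can turn a drug added in follow-up into a baseline drug, and the increase disappears.

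In an on-medication trial, a change in antihypertensive drugs during blinded follow-up is a natural rival explanation for a difference between RDN and control. The medication summaries are where a reader would look for it. If one arm had more additions than the other, hidden additions would also be unequal between arms. Whether that happened cannot be known from the SAP.

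**Working it through.** The SAP gives no figure to reproduce. The check applies the rules literally to example dates, then asks how often they misplace a date.

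**Example dates, SV2 = 16 Mar 2020**

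| Known part | True date | 6-month visit | Imputed date | Recorded as |
|---|---|---|---|---|
| Stop 2020 | 10 Dec 2020 | 1 Oct 2020 | later of 1 Jan and SV2 = 16 Mar 2020 | off at 6 months |
| Stop Oct 2020 | 28 Oct 2020 | 14 Oct 2020 | 1 Oct 2020 | off at 6 months |
| Start 2020 | July 2020 | - | 1 Jan 2020 | baseline drug |
| Start Mar 2020 | 25 Mar 2020 | - | 1 Mar 2020 | baseline drug |

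**Assumptions (not in the SAP).** SV2 is uniform over the calendar year. The procedure is 2-6 weeks after SV2 and the 6-month visit 180 days after that, so the visit falls 194-222 days after SV2 (midpoint 208). An added drug starts uniformly between SV2 and the visit. A drug still taken at 6 months stops uniformly over the next H days, with H = 180, 365 or 913. The last is the 30 months from the 6-month to the 36-month visit: 30 × 365/12 = 913.

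**Stop dates.** The error occurs when the true stop lies in the same calendar year (or month) as the visit, because the first day of that period is then on or before the visit. The SV2 and start-date floors do not prevent it, since both precede the visit.

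- Year-only, H ≤ 365: 1 − (H + 1)/(2 × 365). H = 180: 1 − 181/730 = 0.75. H = 365: 1 − 366/730 = 0.50.
- Year-only, H = 913: (365 − 1)/2 ÷ 913 = 182/913 = 0.20.
- Month-only, average month 365/12 = 30.4 days: (30.4 − 1)/2 ÷ H = 14.7/H. H = 180: 0.08. H = 365: 0.04. H = 913: 0.016.

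**Start dates.** The error occurs when the true start lies in the same year (or month) as SV2.

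- Year-only: 1 − 209/730 = 0.71.
- Month-only: 14.7/208 = 0.07.
- Wholly missing: always, because the date is set to SV2.

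Simulation of the literal rules gives the same values. Taking fixed gaps of 180 or 210 days from SV2 to the visit moves the start-date shares only to 71-75% and 7-8%.

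**The opposite rule.** If stop dates were simply rounded up to the last day of the known period, a drug truly stopped between SV2 and 6 months would be recorded as still taken in about 71-75% of year-only and 7-8% of month-only records. Reversing the rounding alone moves the error to other drugs.

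**The case against.** Much can be said for leaving this alone. Only incomplete dates are affected, and they may be few. An ongoing drug with no stop date is not touched by the rows shown. With only the day missing, the error arises only when the date shares a month with SV2 or the 6-month visit. First-of-period start dates are conventional, and Appendix I treats adverse event onset similarly. Subjects enter on antihypertensives, so placing a wholly unknown start at SV2 is reasonable by default. The rules are blind to arm. The SAP also does not say that the by-visit summaries or the class count come from imputed dates rather than from visit records. All of this stands, and it limits the point to a secondary one.

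Three stronger readings are tempting, and the SAP does not support them.

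- **The primary result is biased.** The primary analysis (9.9.3, 9.9.4) uses 24-hour SBP change and baseline BP, not medication dates.
- **A drug added after SV2 with year-only start and stop never appears in follow-up.** With SV2 in August 2020, start 2020 and stop 2021, the imputed stop is 1 January 2021, so the drug counts from SV2 to then. With SV2 in November 2020 and both years 2021, it appears on 1 January 2021.
- **Any false change in medication burden decides a win-ratio pair.** Only pairs tied on 24-hour SBP (difference under 5 mmHg in the main analysis, or missing data) reach that step, and drug testing takes precedence. A false change matters only if it creates, removes or reverses the pair's difference in burden.

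What survives is that the rules as written can misstate exposure in planned analyses and contain no check that would catch it.

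**Conclusion.** The point holds as a modest, specific weakness. For incomplete dates, a drug still taken at 6 months can be recorded as stopped in about 20-75% of year-only and 2-8% of month-only records. The high end assumes that the true stop came within 6 months after the visit, the low end that it was spread over the following 30 months. A drug added in follow-up can be recorded as a baseline drug in about 71% and 7%. These are shares of the incomplete records concerned, not of all drugs or subjects. They rest on uniform timing, and the total effect is unknown because the number of partial dates is not given.

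The exposed analyses are medication use by visit and medication changes within 6 months (9.7, 9.9.8), the baseline class-count subgroup (9.11) and the win-ratio medication step for tied pairs without drug testing. The populations in 9.1.3.3 and 9.1.3.4 are exposed only if the list of drugs prescribed at SV2 is derived from dates. In that case a later addition wrongly placed at SV2 could make a compliant subject look non-adherent.

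**What to change.** Reword the medication start and stop tables in Appendix I.

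- **Partial stop date:** impute the last day of the known month or year, capped at last contact or data cut. It must not fall before the last visit at which the drug was recorded as ongoing, nor after the first visit at which it was no longer recorded. The second limit is needed to avoid the opposite error shown above.
- **Partial or unknown start date that could fall on either side of SV2:** consult the SV2 medication record. If the drug is not listed there, impute the earliest possible date after SV2. Otherwise keep the present rule.
- **Still ambiguous relative to SV2 or the 6-month visit:** report the medication-change results under both bounds.

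It would also help to state whether the by-visit summaries, the class count and the SV2 prescribed list come from visit records or from dates, and to report the number of imputed dates by arm.

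The cost is two reworded tables and a small programming change. No new data are needed provided visit-level medication records exist, as the summaries at each follow-up in 9.7 suggest. Some misdating will remain where those records do not settle the date.

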9.1.3.3. Per Protocol Population

All randomized subjects, meeting the following criteria:

1. Subjects showing medication compliance in blood and/or urine (via drug testing data) at SV2, 3-months, and 6-months, compared with prescribed AH Meds at SV2.
2. Exclude subjects with protocol deviation code 101 (consent not obtained).
3. Exclude subjects who do not meet the following Inclusion/Exclusion criteria:
 - Inclusion: Individual has an office SBP ≥ 150 mmHg and < 180 mmHg and an office DBP ≥ 90 mmHg measured at SV2, according to the guidelines in Appendix L7 of the study protocol.

- Inclusion: Individual has a 24-hour ABPM average SBP ≥ 140 and < 170 mmHg measured at SV2, according to guidelines in Appendix L7 of the study protocol.
 - Exclusion: Individual has undergone prior renal denervation.
 - Exclusion: Individual has renal artery anatomy that is ineligible for treatment.
4. Exclude subjects meeting the anti-hypertensive medication escape criteria (office SBP ≥ 180 mmHg OR < 115 mmHg associated with symptoms of hypotension or safety concern requiring medication changes).
 5. Exclude subjects who did not receive the treatment they were randomized to.

Office and ambulatory blood pressure outcomes out to 6 months follow-up will be presented for this population.

9.1.3.4. Medication Adherence Population 1

All randomized subjects, meeting the following criteria:

1. Subjects showing medication compliance in blood and/or urine (via drug testing data) at SV2, 3-months, and 6-months, compared with prescribed AH Meds at SV2.
2. Exclude subjects meeting the anti-hypertensive medication escape criteria (office SBP ≥ 180 mmHg OR < 115 mmHg associated with symptoms of hypotension or safety concern requiring medication changes).
3. Exclude subjects who did not receive the treatment they were randomized to.

Office and ambulatory blood pressure outcomes out to 6 months follow-up will be presented for this population.

9.1.3.5. Medication Adherence Population 2

All randomized subjects, meeting the following criteria:

1. Subjects showing medication compliance in blood and/or urine (via drug testing data) at 3-months and 6-months, compared with drug testing AH Meds at SV2.
2. Exclude subjects meeting the anti-hypertensive medication escape criteria (office SBP ≥ 180 mmHg OR < 115 mmHg associated with symptoms of hypotension or safety concern requiring medication changes).
3. Exclude subjects who did not receive the treatment they were randomized to.

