The ITT population, including the full feasibility cohort, will be used. For medication INDEX2, drug testing data will be used at SV2 and 6-months if available, otherwise the medication burden will be determined using prescribed medication data.

Two additional win ratio sensitivity analyses will be performed using thresholds of 3.5 and 0 mmHg for the 24Hr SBP endpoint and keeping the threshold of zero for the medication burden endpoint. The R package BuyseTest version 2.2.6 will be used to perform these analyses.

9.9.10. % Time in Target Range (TTR%) Analyses

Time in target range (TTR%) analyses [16], which calculate the percentage of time that a subject's BP is within pre-specified BP ranges will be calculated by performing linear interpolation over the days between successive BP measurements, including data from both the baseline and follow-up periods, and summarizing over the entire follow-up time period. Subjects must have a minimum of 2 BP measurements within the TTR time interval to be included in the calculation. All follow-up visits will be included in the TTR analyses. Office SBP TTR will be evaluated using a range of ≤ 140 mmHg and 24Hr SBP TTR will be evaluated using ranges of ≤ 140 & ≤ 130 mmHg. In addition, we will combine Office TTR (≤ 140 mmHg) with 24Hr SBP TTR (≤ 130 mmHg) by taking the maximum value for each subject within the TTR time interval.

For each subject we will calculate their TTR%, using the BP endpoints and BP ranges specified above, in the following time intervals:

- TTR% from baseline to 6-months
- TTR% from baseline to 12-months
- TTR% from baseline to 24-months

- TTR% from baseline to 36-months

These results will be tabulated and compared between treatment arms using non-parametric Kruskal-Wallis tests.

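### Appendix I moves every partial medication stop date to SV2 or later, even when the recorded month or year shows that the drug ended before SV2

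*SAP*

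**What the plan says.** SAP 12.1 has a table titled "Imputation of Missing Medication Stop Date". It labels the recorded part of the date as valid and gives a value for the missing part. Two rows matter here:

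- Year known, day and month missing: "Set date = later of (January 1st of that year, SV2 date, start date").
- Month and year known, day missing: the day is first set to the first of that month, "then set the day = later of (New date, SV2 date, start date").

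Both floors, SV2 and start date, are unconditional. The start-date table differs. Its year-only row reads "Set date = January 1st of that year" with no SV2 floor, so a partial start may fall before SV2. Only a wholly missing start is set to the SV2 date.

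Prescribed medication at SV2 or baseline is then used in several places:

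- In 9.1.3.3 (Per Protocol) and 9.1.3.4 (Medication Adherence Population 1), drug-test compliance is judged "compared with prescribed AH Meds at SV2".
- The subgroups in 9.11 include "1 vs. 2 vs. 3 prescribed AH medication classes at baseline".
- In 9.9.9, the win-ratio medication burden uses drug-test data at SV2 and 6 months if available, "otherwise the medication burden will be determined using prescribed medication data".
- Section 9.7 summarizes antihypertensive use at baseline and at each follow-up.

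**The concern.** A floor at SV2 makes sense when the recorded period leaves open whether the drug stopped before or after SV2. It makes no sense when the recorded month or year is already over by SV2. The record then answers the question, and the rule replaces that answer with a date outside the recorded period. The imputation overwrites the part of the date that the table itself treats as valid.

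What is at stake is the list of drugs a subject is taken to be on at SV2. A drug wrongly kept on that list would be expected to be absent on drug testing. It could also raise the baseline class count if no other current drug shares its class, and it would appear as a drug dropped after SV2. Independent validation of the analysis datasets (section 10) would not detect this, because two programmers who follow Appendix I would produce the same wrong date.

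**Working it through.** The plan gives no figure to reproduce. The check applies the two rows literally.

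**Rule (12.1):** imputed stop = latest of (first day of the recorded month, or 1 January of the recorded year; SV2 date; start date).

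**Single example.** Assume SV2 on 15JUN2019, a stop recorded as 2017 and a start before that.

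- Imputed stop = latest of (01JAN2017, 15JUN2019, start) = 15JUN2019.
- Last date the record allows = 31DEC2017.
- Gap = 365 days (31DEC2017 to 31DEC2018) + 166 days (31DEC2018 to 15JUN2019) = 531 days, or 17 months and 15 days.

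**Set of cases.** Assume SV2 on 15MAR2019, with a recorded start before the stop. The corrected column applies the SV2 floor only if the recorded period includes or follows SV2. It uses the first day of the period otherwise.

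| Recorded stop | As written | Corrected | Does the record settle that the drug ended before SV2? |
|---|---|---|---|
| 2017 | 15MAR2019 | 01JAN2017 | Yes |
| Nov 2018 | 15MAR2019 | 01NOV2018 | Yes |
| Jan 2019 | 15MAR2019 | 01JAN2019 | Yes |
| Mar 2019 | 15MAR2019 | 15MAR2019 | No |
| 2019 | 15MAR2019 | 15MAR2019 | No |
| Jun 2019 | 01JUN2019 | 01JUN2019 | No (after SV2) |

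All 50 recorded months tested from Jan 2015 to Feb 2019 move to 15MAR2019 under the rule as written. The correction changes only the first three rows of the table.

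**Does the drug then count at SV2?** This depends on a convention that the SAP does not state.

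- If in use means start ≤ SV2 ≤ stop, the first three drugs count at SV2 as written and do not count after the correction.
- If it means start ≤ SV2 < stop, they do not count either way.

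Under the strict version the SV2 floor would change nobody's status at SV2, so the inclusive version is the more natural reading. It remains an inference.

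**Interaction with a wholly missing start date.** Take stop 2017, no start date and SV2 on 15JUN2019. The start is set to 15JUN2019.

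- If only the SV2 floor is lifted: stop = latest of (01JAN2017, start 15JUN2019) = 15JUN2019, and the problem remains.
- If the start-date floor is lifted as well: stop falls in 2017 and start on 15JUN2019, so the stop precedes the start.

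The correction therefore has to cover the start default for these records too.

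**The case against.** The strongest case on the other side is that the rule may never meet a record it harms. The SAP does not say that the medication log holds drugs ended before SV2. A log limited to drugs active at SV2 or later would fit both the stop-date floor and the default of a missing start to SV2. The AE-onset table has a similar floor at informed consent, where it matches the collection period in 9.10. This stands as to size: the count is unknown and may be zero. It does not rescue the wording, because no such limit is stated for medications, and the partial start-date rows allow dates before SV2.

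A reader might infer more than the SAP supports:

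- **That the drug necessarily becomes prescribed at SV2.** This needs the inclusive convention. It also needs the SV2 prescribed list to be built from imputed log dates, which the SAP does not say.
- **That one such record fails a subject on compliance.** Sections 9.1.3.3 and 9.1.3.4 do not say that every listed drug must be detected. The version history (5.1) places the algorithms for drug-testing values in the table specifications, which are not available here.
- **That the win ratio is tilted toward denervation.** Prescribed data are only the fallback, and burden decides only pairs tied on 24-hour SBP. A stop before SV2 also predates randomization, so a false fall in burden can arise in either arm.

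The extract ends within the stop-date table. Nothing is inferred from the absence of a row for wholly missing stop dates.

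**Conclusion.** The rule is wrong as written for any partial stop date whose recorded month or year ends before SV2: the imputed date contradicts the record. This follows from the text alone.

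The effect on results is conditional. It needs three things: such records exist, the SV2 prescribed list uses imputed dates, and a stop on SV2 counts as in use. If all three hold, subjects could be misclassified in the places listed above. The Per Protocol population carries a secondary Bayesian analysis of the primary endpoint (9.9.4). Both it and Medication Adherence Population 1 carry the frequentist ANCOVA (9.9.6) and the secondary efficacy analyses (9.9.7).

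The primary ITT analysis of 24-hour SBP does not use the SV2 prescribed list. Medication Adherence Populations 2 and 3 take SV2 drug testing as their reference. Neither is touched by this route. The expected harm is misclassification, not a shift toward one arm. Severity is minor.

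**What to change.** In both stop-date rows of Appendix I:

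1. Apply the SV2 floor only when the recorded month or year includes or follows SV2.
2. If the recorded period ends before SV2, impute a date inside that period, not earlier than a recorded start date.
3. For those records, do not set a wholly missing start date to SV2. Set it no later than the imputed stop date, so that the stop never precedes the start and the drug is not counted as in use at SV2.

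It would also help to state whether a stop on the SV2 date counts as in use at SV2.

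The cost is one condition in the stop-date rows, a matching exception in the start-date row, and the same change in the medication dataset program. Records that are ambiguous around SV2, or that stop after it, keep their current dates. If no partial stop date lies wholly before SV2, no result changes.
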